The primary hypothesis is that the classroom-level sensitization intervention will be associated with a higher referral rate into the host trial, compared with referrals arising from school-level sensitization activities in isolation.

The secondary hypotheses are:

- Compared with the control condition, the intervention condition will be associated with a greater proportion of referred students who meet eligibility criteria for inclusion in the host trial.
- Compared with the control condition, the intervention condition will be associated with a greater proportion of students who self-refer.
- Compared with the control condition, the intervention condition will be associated with adolescents reporting a greater severity of total symptoms experienced and a greater severity of internalising and externalising symptom types.

Outcome	Outcome Explanation						
PRIMARY OUTC							
Referral rate into the host trial	The referral rate will be calculated as the number of referred students from a given condition divided by the total number of students in corresponding classes. This will be calculated from researchers' referral logs. Referrals will be recorded continuously and reported for each 4 weeks' time period, for the total study duration of 12 weeks. It will be entered as a binomial variable at the student level indicating if student was referred during the trial	Referral logs					
SECONDARY OU	TCOMES						
Eligibility rate	Eligibility rate is defined as the proportion of referred participants meeting eligibility criteria for the host trial, as a function of the number of referred adolescents in a given condition. Host trial eligibility criteria are as follows: (i) Total Difficulties score on the adolescent-reported Strengths and Difficulties Questionnaire (SDQ) >/= 19 for boys & >/= 20 for girls (2); (ii) SDQ Impact Supplement score of >/=2; and (iii) chronicity of mental health problems for >/= 1 month. Referred students will complete the SDQ as part of the host trial's screening assessment, within 7 working days of the referral date. Eligibility rate will be calculated for each of the 4-week time periods and reported for the entire study duration of 12 weeks. It will be entered as a binomial variable at the student level indicating if referred student is "eligible" to receive counselling.	Adolescent reported SDQ					

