3.1 Trial Design

The trial will be implemented as a Stepped Wedge Cluster Randomised Controlled Trial (SW-CRCT). The essential feature of a SW-CRCT is that random allocation determines the time period in which clusters begin an intervention. All clusters start with the first time period of control intervention, and cross-over from the control to the intervention condition across pre-defined time periods, in a random, but sequential, order(4).

We will select 70 classes using stratified randomisation to represent each of the grades 9th, 10th, 11th, 12th across the six participating schools in Delhi with probability proportional to size.

		Step 1	Step 2	Sequence of receiving treatments*
Sequence 1 (1-35 classes)	Control condition	Intervention condition	Intervention condition	011
Sequence 2 (36-70 classes)	Control condition	Control condition	Intervention condition	001
Time	1 st time period (4 weeks)	2 nd time period (4 weeks)	3 rd time period (4 weeks)	

Figure 1: Illustration showing implementation of the control and intervention conditions.

Notes: The white boxes indicate the group of classes in the control condition and the coloured boxes indicate the group of classes in the intervention condition. *0=control condition; 1=intervention condition The 70 classes will be randomised to be a part of either of 2 sequences as shown in Figure 1. A small block size of 2 will be used to allocate the 70 classes across the two sequences in order to ensure balance, as the number of classes within each grade from the individual schools is relatively small. In the rare instance that a selected class has been dissolved or merged with another class, the next class in the random list will be included to replace the unavailable class. Each sequence will be implemented over three consecutive 4-week intervals. The trial will be conducted over 12 weeks except for breaks due to exams and holidays. All classes will begin with the control intervention period of 4 weeks, where only school level activities will be rolled out.

Notes: The white boxes indicate the group of classes in the control condition and the coloured boxes indicate the group of classes in the intervention condition.

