Control condition. This will comprise whole-school sensitization activities. The supervisor will meet the principal of each school individually to inform them about planned counselling and research activities and to seek their cooperation for the same. This meeting will also provide structured information about common mental health problems faced by adolescents, and address any concerns related to planned procedures and resource demands. Teachers will be invited to participate in separate group sensitization meetings (up to 30 teachers at a time). A standardized script will mirror the topics covered in the meetings with the school principals, but with additional emphasis placed on referral procedures for the host trial. Up to three meetings will be held in each school to maximize coverage of teaching staff. The meeting will be conducted by the same counsellor and researcher pairing responsible for delivering the classroom intervention. Posters will be placed in highly visible locations such as noticeboards or common corridors, in addition to signage on the drop-box, which will remind students (and teachers) of the counselling service.

Across both the conditions, students deemed ineligible for participation in the host trial will be allowed to re-refer themselves after a gap of 4 weeks, offering a suitable time period to re-assess mental health status in line with the host trial's inclusion criterion about symptom chronicity.

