4.2 Outcome variables

The following outcome variables will be prepared at the student level. All individual data pertaining to the variables of referral, referral source, and assessment using SDQ, will be collected only from referred students. Data will be organised in the long format and record the following variables. A codebook will be developed explaining all the variables included in the data sheet.

- Time period of receiving classroom sensitization
- Referral status in each of the three time periods of the trial
- Date of referral
- Eligibility to receive counselling for all referred students (binary variable), determined through the following (table 1):
 - Total Difficulties score on SDQ
 - o Impact score
 - Chronicity
- Scores for symptom sub-types:
 - Externalising score = the sum of the conduct and hyperactivity scales
 - Internalising score = the sum of the emotional and peer problems scales
- Source of referral: categorized as self-referral and others

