We have data with three records for each student, for time period 1, 2 and 3, with students nested in classes. The calculation of the parameters will need to account for this clustering of data at the class level. Analysis will be undertaken using Generalized Estimating Equations (GEE) with robust standard errors that are measured using the sandwich estimator method. GEE is a general statistical approach to fit a marginal model for longitudinal/ clustered data analysis. GEE was introduced by K. Liang and S. Zeger(13) to analyse longitudinal data without resorting to fully specified random effect models and can be applied to both continuous and categorical outcomes. It is a recommended method for analysis of the stepped wedge cluster randomised controlled trials(14), and provides population averaged effects of exposure to the interventions across the control and intervention conditions. GEE provides both parameter estimates and standard errors that are corrected for clustering of data and are consistent despite misspecifications in the correlation structure. For these reasons, GEE is a suitable method for analysis of primary outcome in this trial.

The analysis will be carried out using "xtgee" command using Stata 15.1. The panel structure of data and clustering of data at class level will be specified through stata command "xtset". The following will be specified in the GEE model:

- Family of distribution of the response variable: Binomial as the outcome variable is binary.
- Link function: Logit link function.
- The within-group correlation structure will be specified as independent.
- Standard error type: robust.

Having a variable for indicating the class in which student observations are nested (class_id), outcome variable indicating the referral status of the adolescent (referred), time indicator (t2) for period 2 for classes that continue to experience school based sensitization activities, indicators for the immediate and continued effects of classroom sensitization activities (effect_lag0 and effect_lag1), the parameters will be estimated using the stata command as illustrated below:

"xtset class_id"

"xtgee referred t2 effect_lag0 effect_lag1, family(binomial) link(logit) corr(independent) vce(robust)"

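### The primary model scores every student in all three periods with no first-referral or at-risk rule and takes period 1 as its reference, so depletion of referable students falls on the intervention side.

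*SAP*

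**What the plan says.** **Records.** SAP section 6.2 sets the outcome to 1 if the student is referred in period l and 0 otherwise, and adds: "We have data with three records for each student, for time period 1, 2 and 3, with students nested in classes". Section 4.2 lists the matching data item: "Referral status in each of the three time periods of the trial". No section drops a student's records after a referral or says whether the first or every referral counts.

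**Table 1.** The referral rate is the number referred from a condition "divided by the total number of students in corresponding classes", reported by 4-week period. The same cell then says: "It will be entered as a binomial variable at the student level indicating if student was referred during the trial".

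**Re-referral.** Section 3.4, for both conditions: "students deemed ineligible for participation in the host trial will be allowed to re-refer themselves after a gap of 4 weeks". It gives no rule for students found eligible. Section 3.1: "Each sequence will be implemented over three consecutive 4-week intervals". The waiting time therefore equals one period.

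**Model.** The regressors in the section 6.2 command are t2, effect_lag0 and effect_lag1. Section 6.2 defines t2 as marking only the classes still in control in period 2. The reference is period 1.

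**Sensitivity analysis.** Section 6.4 compares the two sequences in period 2 only.

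**The concern.** A student referred in period 1 and found ineligible cannot be referred again for part or all of period 2, yet is scored 0 there as if freely referable. After the gap the same student can score 1 again, so one student may count once under control and once under intervention.

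The first mechanism lowers later periods and the second raises them. They cancel only if previously referred students are referred as often as the rest.

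The model does not absorb the difference. Period 1 is all control with nobody yet referred in the trial, while every immediate-intervention cell lies in period 2 or 3. Because t2 marks one control cell and not the whole period, the main parameter is simply those later cells against period 1. A depletion effect then reads as a weaker intervention effect, and it moves the estimate off 1 even when the classroom session does nothing.

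**Working it through.** **Inputs.** From SAP section 3.6: 5% control, 15% intervention, ICC 0.124 with the same between-time correlation, 70 classes of about 50, so 35 × 50 = 1750 students per sequence. I read the rates as per-period probabilities for a student not yet referred. Let r be the referral probability of previously referred students relative to the others. The SAP does not give r, so a range is shown.

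**Planned effect.** OR = (0.15/0.85)/(0.05/0.95) = 3.35. (Section 3.6's 92% power is not used here.)

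**What the main parameter estimates.** The three regressors are mutually exclusive indicators. With independence working correlation and equal-sized sequences, the immediate OR is the odds of the mean of sequence 1 period 2 (S1P2) and sequence 2 period 3 (S2P3), over the odds in period 1.

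**1. Identical classes, r = 0**
- S1P2 = 0.15 × 0.95 = 0.1425
- S2P3 = 0.15 × 0.95² = 0.1354
- mean 0.1389; OR = (0.1389/0.8611)/(0.05/0.95) = **3.07**; difference 8.9 points instead of 10
- no true effect: mean = 0.05 × (0.95 + 0.9025)/2 = 0.0463; OR = **0.92**
- continued effect without waning: S1P3 = 0.15 × 0.95 × 0.85 = 0.1211; OR 2.62 instead of 3.35. If the rate truly returned to 5%: 0.05 × 0.95 × 0.85 = 0.0404; OR 0.80 instead of 1.0

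**2. Identical classes, some re-referral.** S1P2 = 0.15 × [1 − (1 − r) × 0.05]; S2P3 = 0.15 × [1 − (1 − r) × 0.0975].

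| r | Mean rate | Immediate OR |
|---|---|---|
| 0 | 0.1389 | 3.07 |
| 0.25 (e.g. half ineligible, returning at half the rate) | 0.1417 | 3.14 |
| 0.5 | 0.1445 | 3.21 |
| 1 | 0.1500 | 3.35 |

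At r = 0.5 the repeat referrals number 1750 × 0.05 × 0.5 × 0.15 ≈ 7 in S1P2 and 1750 × 0.0975 × 0.5 × 0.15 ≈ 13 in S2P3.

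**3. Persistent class differences at ICC 0.124, r = 0.** I assume beta-distributed class rates c (control) and t (intervention), with each class at the same quantile of both. High-referral classes then lose more students.
- E[c²] = 0.05² + 0.124 × 0.05 × 0.95 = 0.00839
- beta parameter sum 1/0.124 − 1 = 7.065, first parameter 0.353; E[c³] = 0.00839 × 2.353/9.065 = 0.00218
- no true effect: S1P2 = 0.05 − 0.00839 = 0.0416; S2P3 = 0.05 − 2 × 0.00839 + 0.00218 = 0.0354; mean 0.0385; OR = **0.76**
- planned effect: numerically E[tc] = 0.0167 and E[tc²] = 0.0037, so S1P2 = 0.1333, S2P3 = 0.1203, mean 0.1268; OR = **2.76** (a simulation of the trial gave 2.80)

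**4. Dropping later records, changing nothing else (ICC 0.124, r = 0).** The remaining fractions are 0.95 and 1 − 0.10 + 0.00839 = 0.9084.
- no true effect: (0.0416 + 0.0354)/(0.95 + 0.9084) = 0.0414; OR 0.82
- planned effect: (0.1333 + 0.1203)/1.8584 = 0.1365; OR 3.00

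For comparison, all records at r = 0.25 under no effect give mean 0.05 − 0.75 × (0.05 − 0.0385) = 0.0414, again OR 0.82. An at-risk rule alone does not cure the problem.

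**5. Comparison within period 2.** Both sequences carry the same control history.
- identical classes, all records: 0.1425 against 0.0475; OR 3.33
- no true effect: equal rates, OR 1.0, at either ICC
- ICC 0.124, first referrals only: 0.1333/0.95 = 0.1403 against 0.0416/0.95 = 0.0438; OR about 3.56, somewhat above 3.35

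**The case against.** **The whole-class denominator is the declared estimand.** The primary objective in section 3 and Table 1 both divide by all students, so a lower class-wide rate in later periods is part of what is measured. This stands against calling the denominator an error. It does not rescue the contrast: with no intervention effect the main parameter still departs from 1, because later periods are set against period 1.

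**Section 6.4 covers it.** It largely does, and the power calculation rests on that comparison. But it is a sensitivity analysis, and the primary result could differ from it for a reason unrelated to the intervention.

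**Table 1 contradicts section 6.2.** A reader might infer this from "indicating if student was referred during the trial". The full cell also speaks of referrals from a given condition and of 4-week reporting, so the sentence is loose wording that needs aligning, not proof of a second outcome.

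**Eligible students are fixed zeros to the end.** This too is tempting, but section 3.4 states no rule for them. It can only be inferred from their moving to the host trial. The wait for ineligible students also depends on individual dates and may cover only part of the next period. So r = 0 is the extreme case, not the expected one.

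**Conclusion.** The defect stands: the SAP leaves first against repeat referrals undefined and contrasts later intervention cells with an undepleted period 1. At the planned rates with no re-referral, the immediate OR is 3.07 with identical classes and about 2.76 at ICC 0.124, against 3.35. With no effect it is 0.92 and about 0.76. These figures rest on per-period rates of 5% and 15%, equal sequence sizes and, for the second figure of each pair, the beta model. With identical classes the shift falls to zero as r rises to 1. It is larger at higher control rates: at 10% against 20% with r = 0 and identical classes, the mean is 0.20 × (0.90 + 0.81)/2 = 0.171, and the OR falls from 2.25 to 1.86.

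A reader might conclude that the primary result must be badly biased, or that dropping later records suffices. The documents do not support the first, since r is unknown. The ICC calculation does not support the second.

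**What to change.** 1. In section 6.2, define the outcome as the student's first referral in the 12 weeks, assigned to the period of its referral date. Keep records up to and including that period.
2. Align Table 1 with this, in both outcome wording and denominator (students not yet referred at the start of the period).
3. Replace t2 with common indicators for periods 2 and 3, so that conditions are compared within period.
4. Report re-referrals descriptively, by period and condition.
5. Do not restrict the eligibility outcome to the first assessment without stating how students found eligible on re-referral are counted.

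**Cost.** Wording and one data-preparation step; referral dates and student IDs are already collected. The estimate becomes a per-period probability among students not yet referred. Some precision is lost: with both period indicators and both effect terms, period 3 has two cells and two parameters of its own (its period term and the continued effect), so the immediate effect is estimated from period 2 alone. That is the comparison section 3.6 powers, but section 6.4 then differs from the primary analysis only in keeping all records, and the SAP should say so.

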3.6 Power calculation

We based our power calculation on a within-period comparison for a stepped wedge design(10), using Stata package "clustersampsi". Based on pilot data, we anticipated referral rates of 5% and 15% on the control and intervention conditions respectively, with an intra-cluster correlation coefficient (ICC) of 0.124. We assumed the same ICC for the between-time correlation given the short time period of follow-up. In practice, it may be smaller than 0.124 and both ICCs will be reported. Using these parameters, a sample size of 70 classes (average class size of 50 students) will have 92% power to detect a difference of 10 percentage points (treating the outcome as a binomial variable), at a significance level of 0.05.

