6.2 Analysis of primary outcome

In this section, we describe the statistical analysis for the primary outcome. The intervention delivery in the intervention condition at class level (cluster). As we know the size of classes and have the data for all the referred students in each of the time periods, we are able to construct the data at the individual level:

$$Y_{ijk} = \begin{cases} 1 & if \ student_{ijk} \ referred \\ 0 & else \end{cases}$$

where i = 0 or 1 (0 = control condition, 1 = intervention condition), $j = 1, ..., m_i$ (number of classes in each condition), $k = 1, ..., n_{ij}$ the number of students in class j in condition i. We therefore have observations nested within students and students nested within classes. The primary analysis takes data of all three time periods into account. So, we have

$$Y_{ijkl} = \begin{cases} 1 & if \ student_{ijk} \ referred \ in \ period \ l \\ 0 & else \end{cases}$$

where l = 1, 2 or 3 to indicate the period.

Figure 3: Trial schematic indicating the effects that can be measured (adapted from figure 1)

		Step 1	Step 2
Sequence 1 (1-35 classes)	Control condition (immediate control effect)	Intervention condition (immediate intervention effect)	Intervention condition (continued intervention effect)
Sequence 2 (36-70 classes)	Control condition (immediate control effect)	Control condition (continued control effect)	Intervention condition (immediate intervention effect)
Time	1 st time period (4 weeks)	2 nd time period (4 weeks)	3 rd time period (4 weeks)

We can describe the following effects of the intervention (figure 3):

- The classes in sequence 1 and sequence 2 underwent the immediate effect of the school level sensitization intervention (control condition) at the first period.
- The classes in sequence 1 and sequence 2 underwent immediate effects of receiving classroom sensitization intervention (intervention condition) in the second and third time periods respectively the main parameter of interest.
- The classes in sequence 2 underwent continued effects of receiving school level sensitization intervention (control condition) in second time period.
- The classes in the sequence 1 underwent continued effects of receiving the classroom sensitization intervention (intervention condition) in the third time period.

These effects can be described in the following equation

$$logit\left(P(Y_{ijkl})\right) = \theta_0 + \theta_1 X_{li} + \theta_2 T_{2l} + \theta_3 T_{3l}$$

Where:

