 Y_{ijkl} is as before, $logit(P(Y_{ijkl}))$ is the log odds of being referred to the counselling program

 θ_0 is a constant that reflects the immediate effect of school-level activities (for all classes in first time period),

 θ_1 reflects the immediate effect of the classroom activities and is the main parameter of interest (corresponding to the classes receiving the classroom intervention - classes of sequence 1 in the second time period and classes of sequence 2 in the third time period),

 θ_2 reflects the continued effects of the school-level activities (corresponding to the sequence 2 classes continuing in the control condition in second time period),

 θ_3 reflects the continued effect of the classroom activities (corresponding to the classes of sequence 1 continuing in the intervention condition in the third time period)

 X_{li} is an indicator for the time periods when classroom intervention in introduced (equals 1 if i = 1 and l = 2 (sequence 1 classes that received classroom intervention at period 2) or if i = 1 and l = 3 (sequence 2 classes that received classroom intervention at period 3)),

 T_{2l} is an indicator for second time period where classes of sequence 2 experienced continued effect of school sensitization activities (equals 1 if i = 0 and l = 2),

 T_{3l} is an indicator for the third time period where classes of sequence 1 experienced continued effects of the classroom sensitization intervention (equals 1 if i = 0 and l = 3)

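### The primary GEE has no common period terms, so θ1 is confounded with calendar time; once they are added, the independent working correlation reduces the primary analysis to the period-2 sensitivity analysis

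*SAP*

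**What the plan says.** On the model, SAP section 6.2 states that "The primary analysis takes data of all three time periods into account". The printed command is "xtgee referred t2 effect_lag0 effect_lag1, family(binomial) link(logit) corr(independent) vce(robust" (final bracket cut here). Its terms are narrow:

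- `t2` is the indicator "for period 2 for classes that continue to experience school based sensitization activities", so it marks sequence 2 in period 2 only.
- `effect_lag0` carries θ1, the main parameter. It covers "classes of sequence 1 in the second time period and classes of sequence 2 in the third time period".
- `effect_lag1` is the continued effect, that is, sequence 1 in period 3. (The printed condition for T3, i = 0 and l = 3, does not match this description; I follow the description and the command.)

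On correlation, section 6.2 says "The within-group correlation structure will be specified as independent", with robust standard errors. It justifies GEE on the ground that estimates and SEs "are consistent despite misspecifications in the correlation structure".

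On planning values, section 3.6 says "we anticipated referral rates of 5% and 15% on the control and intervention conditions respectively", with an ICC of 0.124, 70 classes of 50 and 92% power from a within-period comparison. It adds: "We assumed the same ICC for the between-time correlation given the short time period of follow-up". It then allows that the between-period value may prove smaller.

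Section 6.4 repeats the comparison in period 2 only, as a check on the primary result.

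**The concern.** Two choices interact. First, the only reference category in the printed model is period 1. Anything that moves referrals between period 1 and later periods, such as the exam and holiday breaks foreseen in section 3.1, enters θ1. The plan itself allows the control rate to differ between periods 1 and 2, through θ2. Yet it does not apply that shift to the sequence 1 classes in period 2, and it has no counterpart for period 3. If θ2 is not zero, the randomised period-2 contrast is θ1 − θ2, not θ1.

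Second, the natural repair is to add period indicators for all classes. Period 1 is all control and period 3 all intervention, so only period 2 then holds both conditions. With an independent working correlation, each class's period-1 record no longer informs θ1. At stake are the randomised basis of the primary estimate, the precision offered by 70 control-period records, and the separate role of section 6.4.

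**Working it through.** **Inputs (section 3.6):** p0 = 0.05, p1 = 0.15, within-period ICC ρ = 0.124, m = 50, 70 classes, hence 35 per sequence (section 3.1). Between-period ICC = c × ρ, where c = 1 is the SAP's assumption. My assumptions: equal class sizes, two-sided 5% test, and a same-student correlation between periods equal to the between-period ICC.

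**The plan's own figure.** A within-period comparison of 35 v 35 classes, in coefficient-of-variation form with k² = ρ(1 − p)/p at p = 0.10:

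- k² = 0.124 × 0.9/0.1 = 1.116
- Variance per pair of classes = 0.0475/50 + 0.1275/50 + 1.116 × (0.05² + 0.15²) = 0.0035 + 0.0279 = 0.0314
- z = √(35 × 0.01/0.0314) = 3.34, and Φ(3.34 − 1.96) = 91.6%. Multiplying the between-class part by (1 − 1/m) gives 92.05%.

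The 92% is reproduced, and it uses period 2 alone. (A simple design-effect calculation gives 96.2% and does not match.)

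**Building blocks on the log-odds scale.** D = (1 + 49 × 0.124)/50 = 0.14152. Per class:

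- variance at 5%: D/0.0475 = 2.979
- variance at 15%: D/0.1275 = 1.110
- between-period covariance at c = 1: for 5% with 15%, 0.124/√(0.0475 × 0.1275) = 1.593; for 5% with 5%, 0.124/0.0475 = 2.611

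**Model as printed.** θ1 is the first-exposure record minus the period-1 record, over all 70 classes:

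- Var = (2.979 + 1.110 − 2 × 1.593)/70 = 0.01289, so SE = 0.1136
- Exchangeable working correlation gives the same 0.1136.
- Scale of the confounding: 1.96 × 0.1136 = 0.223 and exp(0.223) = 1.25. A drift of about 25% in the referral odds, common to periods 2 and 3, would shift θ1 by 1.96 SEs with no intervention effect at all.

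**Period indicators for all classes, plus lag 0 and lag 1, independent.** θ1 is the period-2 difference between sequences, with zero weight on periods 1 and 3:

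- Var = (1.110 + 2.979)/35 = 0.1168, so SE = 0.342
- Power: log odds ratio ln[(0.15/0.85)/(0.05/0.95)] = 1.210; 1.210/0.342 = 3.54; Φ(3.54 − 1.96) = 94%

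**Same mean model, exchangeable, c = 1.** θ1 is the period-2 difference minus w times the period-1 difference:

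- w = (1.593 + 2.611)/(2 × 2.979) = 0.7055
- Var = [4.089 − (4.204)²/(2 × 2.979)]/35 = (4.089 − 2.966)/35 = 0.0321, so SE = 0.179
- Ratio 0.342/0.179 = 1.91

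Because lag 1 has its own term, period 3 has no weight on θ1 here either. The whole gain is adjustment for each class's period-1 referral rate.

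**If class effects persist less (exchangeable parameter estimated from the data):**

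| c (between/within ICC) | SE independent | SE exchangeable | ratio |
|---|---|---|---|
| 1 | 0.342 | 0.179 | 1.91 |
| 0.9 | 0.342 | 0.221 | 1.55 |
| 0.8 | 0.342 | 0.256 | 1.34 |
| 0.5 | 0.342 | 0.334 | 1.02 |
| 0.25 | 0.342 | 0.380 | 0.90 |
| 0 | 0.342 | 0.410 | 0.83 |

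At c = 0 the exchangeable SE is 0.410/0.342 = 1.20 times the independent one. A linear calculation with equal variances and the working correlation held at the planning value gives 0.1196/0.0899 = 1.33, which is the upper figure.

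**Sensitivity at c = 1.** A same-student correlation from −0.05 to 0.5 moves the 1.91 to between 1.78 and 2.31. A single intervention term in place of lag 0 and lag 1 gives 2.10.

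**The case against.** The strongest reply is that the precision loss does not occur in the model the SAP prints. That is correct. A reader might infer from sections 3.6 and 6.2 that the planned SE is nearly doubled, but in the printed model periods 1 and 3 both carry weight and the two structures give the same SE. The section 6.4 analysis also differs from the printed 6.2 model, so today it is a real check.

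A reader might also infer that independence contradicts the equal-ICC assumption. It does not. A working correlation with sandwich SEs makes no claim that the ICC is zero, and section 6.2 says as much. The question is efficiency, not validity.

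Nor is planned power lost, since the 92% comes from a within-period comparison. Independence also has something in its favour: it does not depend on a between-period ICC for which the SAP gives no separate pilot estimate and which it concedes may be lower.

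Simulated type I error of 7.2% (independent) and 6.0% (exchangeable) in 500 null trials does not separate the structures; the Monte Carlo error is about 1.1 points each.

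What remains is that the printed model buys its small SE by treating period 1 as the comparator. When that is put right, the correlation line stops being harmless.

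**Conclusion.** The point holds in two linked parts. As printed, θ1 is a before-after contrast confounded with calendar time, whatever the working correlation. With period terms added and independence kept, the primary analysis is valid but identical to section 6.4. Its SE is then about 1.9 times the exchangeable SE under the SAP's equal-ICC assumption and about 1.3 times at a between/within ratio of 0.8, with no gain near 0.5. What is forgone is available precision, not the planned 92% power. The figures rest on 5% and 15% referral, ICC 0.124 and 35 classes of 50 per sequence. The documents do not support the reading that the SAP contradicts itself on the ICC, or that the SE of its printed analysis is inflated. The change is worth making, and should be fixed before outcome data are seen.

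**What to change.** Make both changes together in section 6.2:

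`xtgee referred t2 t3 effect_lag0 effect_lag1, family(binomial) link(logit) corr(exchangeable) vce(robust)`

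Here `t2` and `t3` are period 2 and period 3 indicators for all classes. Rewrite the equation and the definitions of θ0 to θ3 to match. Keep the period-2-only analysis of section 6.4 as the sensitivity analysis; it is what independence would give.

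The cost is more than one option. `t2` is redefined, `t3` is new, and θ1 changes meaning to a comparison adjusted for period. Changing only the correlation option in the printed command would alter nothing. The SE of θ1 will also be larger than in the printed model (0.179 at best, against 0.1136), because the time effect is no longer assumed away. If the between-period correlation is below about half the within-period ICC, exchangeability is less precise than independence: by about a fifth at zero persistence when the correlation is estimated, and up to about a third if it is held at the planning value. Robust SEs remain valid in that case, and section 3.6 already commits to reporting both ICCs, so the reader can see which case applies.
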